Tissue Reinforcement of Incisional Closure Among High Risk Patients

NCT03148496

[figure not shown]
Version Date: 03/06/2020

IRB NUMBER: HSC-MS-17-0063
IRB APPROVAL DATE: 03/06/2020

Tissue Reinforcement of Incisional Closure Among High Risk Patients

[name], [name], [name]
Mentor: [name]

Background

One-third of all individuals will undergo abdominal surgery in their lifetime. [1,2] Following abdominal surgery, 30% of patients will suffer a major chronic complication with their wound closure in the first post-operative year. This may include significant wound infections, open wounds, fluid collections, fascial dehiscence, or incisional hernia. These complications not only have a substantial impact on the health care system (cost and chronic disease) and the hospital (cost and space), but most importantly have a substantial impact on the patient. Major chronic wound complications adversely impact patient quality of life and function. [3-6]

Patients at greatest risk for major wound complications include comorbid patients such those who are overweight or obese, currently smoke or have COPD, are immunosuppressed, are malnourished, or who have evidence of contamination (wound classes 2-4). Among these patients, the risk of developing a major wound complication ranges from 30%-80%. [1,2,7,8,9]

Potential methods to reduce major wound complications include utilizing specific suturing techniques or reinforcing the incision line. Suturing technique of small-bites (0.5x0.5 cm bites) as opposed to large bites (1.0x1.0 cm bites) has been shown to be efficacious in European populations with a typical body mass index of 20-25 kg/m². [10-12] Tissue reinforcement has been shown to decrease rates of major wound complications in small randomized controlled trials. [13-18]

However, the lack of widespread adoption of these practices may be due to issues of generalizability including strict inclusion criteria, careful patient selection, and small study size. For example, the generalizability of small bites to an overweight population (mean BMI in the United States is 28 kg/m²) as opposed to a normal-weight population are unclear. [10-12] The use of synthetic materials in comorbid patients or complex settings may risk major wound complications such as prosthetic infection. Biologic materials have been shown to be effective in decreasing major wound complications but in different settings. [13-19]

Specific Aims

Assess the effectiveness of different efficacious strategies to decrease the rate of major wound complications following abdominal surgery among high-risk individuals.

Hypotheses

1. Among high-risk patients undergoing abdominal surgery, the use of “small-bites” closure as opposed to “large-bites” closure will increase the proportion of patients who are free of major, chronic wound complications at 1-year post-operative.
2. Among high-risk patients undergoing abdominal surgery, the biologic tissue reinforcement of the suture line as opposed to no reinforcement will increase the proportion of patients who are free of major, chronic wound complications at 1-year post-operative.

Methods

This is a single-institution, 2x2 factorial randomized controlled trial assessing the effectiveness of known efficacious treatments (“small-bites” and tissue reinforcement) among high-risk patients undergoing midline laparotomy or laparoscopic-assisted surgery. [19] Laparoscopic-assisted abdominal surgery is defined as any surgery requiring an open incision in addition to laparoscopy to insert a hand (hand-assisted laparoscopy) or specimen extraction site ≥ 3 cm in

length. This length is chosen because any smaller incision will likely be closed with interrupted sutures rather than running sutures.

Table 1: 2x2 Factorial Design for Prevention of Major, Chronic Wound Complication [19]

		Randomization 1	
		Small-Bites	(Current Care) Large-Bites
Randomization 2	Mesh	Small-Bites Mesh	Large-Bites Mesh
	(Current Care) No Mesh	Small-Bites No Mesh	Large-Bites No Mesh

A 2x2 factorial trial design is utilized because it is more efficient (can assess two interventions simultaneously) and mimics real-world practice (e.g. adoption bundle therapies, adoption of multi-faceted interventions). In addition, the 2x2 factorial design remains novel, particularly among surgical literature that can improve profile of studies performed with this approach.

Inclusion criteria will include all high-risk patients undergoing laparotomy or laparoscopic-assisted abdominal surgery. High-risk patients will include (1) all overweight patients, (2) current smokers, (3) those who are immunosuppressed, (4) those who are malnourished, or (5) those who are undergoing a contaminated case. Overweight is defined as $BMI \geq 25 \text{ kg/m}^2$. Current smoker is any patient who routinely smokes within the past month. Immunocompetent is any patient who has or will receive immunosuppressive medications or drugs within 3 months of surgery. Malnourished is defined as albumin $<3.5 \text{ g/dL}$. Contamination is defined as Center for Disease Control wound classification 2 or 3. [20]

Exclusion criteria include (1) patients unlikely to follow-up in a year (e.g. no phone or lives out of state), (2) patients unlikely to survive more than 2 years based upon surgeon judgment (e.g. metastatic cancer, end-stage cirrhosis), (3) patients where the clinician would not place prosthetic (e.g. pregnant patient, pediatric patient during growth stage), (4) patients on full anticoagulation treatment or (5) patient has a planned second surgery within the next year (e.g. ostomy reversal).

Current care for wound closure includes a 1x1 cm closure using a slowly absorbable, running suture (0 polydioxanone). Surveys among surgeons have identified that the vast majority of United States surgeons and surgeons at our institution perform abdominal closure in this technique. "Small-bites" will be performed using a 0.5x0.5 cm closure using a slowly absorbable running suture (2-0 polydioxanone). Mesh placed will be a biologic mesh, (porcine acellular dermal matrix) and will be fenestrated with a scalpel. Preperitoneal space will be chosen for all midline incisions where preperitoneal space can be safely and easily developed (open, lower midline incisions). Underlay will be chosen for all off midline (e.g. stoma site incision) where laparoscopic fixation will be more efficient.

Primary outcome will be proportion of patients at one year with a major chronic wound complication. Major chronic wound complications will include any persistent wound or infection at 1-year post-operative, fascial dehiscence, or fascial defect. Persistent wound or infection will include any enterocutaneous fistula, open wound, or symptomatic fluid collection. Fascial dehiscence or fascial defect will be defined as any defect noted on clinical assessment. Clinical assessment is clinical examination and demand-driven CT scan ordered based upon signs or symptoms including patient complaint of pain, bulge by patient report or physical exam, or wound complication. This represents current practice.[21] In addition, all patients will undergo

an ultrasound performed by a trained clinician to assess for any chronic, major wound complications at one year post-operative. Patients will also be followed for up to three years post-operative.

Secondary outcomes will include any Dindo-Clavien complications, surgical site infections, reoperations, operative duration, patient centered outcomes, surgeon perceptions, and cost analyses. Dindo-Clavien and surgical site infections have been defined.[20,22] Reoperation will be defined as any unplanned invasive procedure involving the fascia, mesh, or peritoneal cavity. Patient centered outcome based upon the modified Activities Assessment Scale and Euroqol-5D will be measured at 1 year and 3 years. Surgeon perceptions will include Likert type and open-ended questions assessing perception, barriers, and likelihood of utilizing the interventions outside of the trial. Cost will be calculated from the hospital's perspective by assessing charges for all patient visits, admissions, and procedures. These charges will be adjusted utilizing department-specific cost-to-charge ratios (CCR). The CCR are the ratios at the cost center level that hospitals are required to submit to Centers for Medicare and Medicaid Services annually (under the hospital's annual Medicare cost report). This will allow charges to be converted to cost by applying these CCRs to charges. Following state-of-the-art guidelines, cost will be discounted at an annual rate of 3%. The robustness of the results will be assessed by performing sensitivity analyses of plausible ranges for the project parameters and probabilistic sensitivity analysis. Follow-up schedule is provided in Table 2.

Table 2: Follow-up Schedule

Timing	Level of Care	Assessments	Reimbursements
1 month	Routine care	Routine care Clinical exam Assessing: Hernia (clinical) Dindo-clavien complications Surgical site infections Patient centered outcomes (modified Activities Assessment Scale and Euroqol-5D)	\$0
1 year	Research follow-up	Clinical exam Assessing: Hernia (clinical and ultrasound) Dindo-clavien complications Patient centered outcomes (modified Activities Assessment Scale and Euroqol-5D)	\$10 gift card \$10 parking
3 years	Research follow-up	Clinical exam Assessing: Hernia (clinical and ultrasound) Dindo-clavien complications Patient centered outcomes (modified Activities Assessment Scale and Euroqol-5D)	\$20 gift card \$10 parking

A trained surgical clinician blinded to the treatment arms will collect outcomes. A blinded outcomes adjudication committee (non-participating members of the Ventral Hernia Outcomes Collaborative) will verify the primary outcome.

A Data Safety Monitoring Board of the Ventral Hernia Outcomes Collaborative will be developed. All major complications (Dindo-Clavien 3-5) including deaths, reoperations, mesh explantations, and enterocutaneous fistulas will be reviewed. No interim analysis will be planned as analysis of the primary outcome will weaken the strength of the results. Safety and stopping points will be determined based upon clinical judgment or greater than 50% rate of major complications.

Enrollment will occur prior to the operation either in the clinic (for elective cases) or on the day of surgery (for urgent or emergent cases). The randomization schema will be variable block randomization with blocks stratified by surgical approach (laparoscopic versus open): this is chosen not because there is belief that there will be a difference in outcomes, but because it is a different surgical approach and should be balanced. Allocation will occur at the time of abdominal closure by phone call to the study office.

Statistical analysis

Based upon prior studies, it is estimated that the risk of a major, chronic wound complication in this population is at least 30% while either intervention would result in a decrease in relative risk by 30% (i.e. absolute risk reduction from 30% to 20%). The risk of complication at 1 year is the same with open or laparoscopic assisted surgery as shown in multiple prior studies. [1,2,26] Assuming an alpha of 0.05, beta of 0.20, and a dropout rate of 20%, a total of 192 300 patients would need to be enrolled and 154 patients randomized. Based upon our current surgical volume of nearly 6000 general surgical procedures performed each year and our track record of enrolling over 400 surgical patients in the past year for three other trials, we anticipate completing enrollment within one year. To encourage patient follow-up, all patients will be provided with up to a \$10 gift card at the one-year follow-up and \$20 at the three-year follow-up along with payments for their parking (\$10) at both one- and three-year visits. [23]

The primary outcome will be assessed as a categorical variable using a chi square test. In addition, analysis will be performed using a Cochran-Mantel-Haenszel method as well as a multivariate regression analysis accounting for the 2 randomizations and the stratification. Secondary outcomes will be assessed either chi-square or Kruskal-Wallis test.

Based upon traditional Frequentist assessment, if the effect size does not achieve “statistical significance” the conclusions risk being reported as a false negative. To address this potential risk, a more real-world, realistic analysis will be performed using a Bayesian analysis will also be performed. [24,25] The Bayesian models will take the same form as the Frequentist models and include the same covariates. Posterior point estimates, credible intervals, and probability of increase in proportion of patients without hernias or complications will be calculated. Similar models will be used for secondary outcomes. **If interactions or modifiers are identified, then this study will be underpowered and should be considered a pilot study to appropriately power future multi-center randomized controlled trials.**

Cost will be calculated by assessing charges for all patient visits, admissions, and procedures. These charges will be adjusted utilizing department-specific cost-to-charge ratio (CCR). The CCR are the ratios at the cost center level that hospitals are required to submit to Centers for Medicare and Medicaid Services annually (under the hospital’s annual Medicare cost report). This will allow charges to be converted to cost by applying these CCRs to charges. Following state-of-the-art guidelines, cost will be discounted at an annual rate of 3% for charges over 1 year. The robustness of the results will be assessed by performing sensitivity analyses of plausible ranges for the project parameters and probabilistic sensitivity analysis.

Feasibility and Significance

Our group has performed three prospective trials (2 randomized trial and one non-randomized trials), have completed enrollment for 2, and am on track to complete enrollment for the final study by March 2017. We have a strong track record of completing all projects that we have initiated ahead of schedule. This study will provide effectiveness data on the role of small bites

and biologic tissue reinforcement on the impact of patient satisfaction, quality of life, and function.

Budget

This study represents an effectiveness study of current practices and recommendations. At present, multiple societies recommend the use of mesh reinforcement and small-bites as best practices. [26] In addition, CMS has established a Current Procedural Code for tissue reinforcement for these cases.

The costs above our group's current practice are (1) ultrasounds performed at 1-year and (2) mesh. The department of surgery owns an ultrasound and the outcomes assessors will be trained on ultrasound of the abdominal wall course with the American College of Surgeons. [27] These cost of mesh have been offset by an investigator-initiated grant (all meshes will be donated by a biologic mesh company). The concerns for conflict of interest will be curbed by (1) the study will be overseen and performed by individuals with no direct benefit from this grant; an individual blinded to the allocations will assess the outcomes that also will receive no direct benefit from this grant.

References

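### Operative duration has no start or stop point, and patients are allocated only at closure: comparing arms on whole-operation time is unbiased but imprecise, and closure time would serve better

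*Combined protocol and SAP*

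**What the plan says.** The secondary-outcome paragraph of the Methods reads "Secondary outcomes will include any Dindo-Clavien complications, surgical site infections, reoperations, operative duration, patient centered outcomes". Operative duration is not defined further. Closure time is not listed there or in the follow-up schedule (Table 2).

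Consent and allocation are separated in time. On consent: "Enrollment will occur prior to the operation either in the clinic (for elective cases) or on the day of surgery". On allocation: "Allocation will occur at the time of abdominal closure by phone call to the study office".

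Both randomized factors are closure techniques. One compares 0.5 cm with 1 cm running bites. The other compares biologic mesh with no mesh, and for the mesh plane the Methods state: "Preperitoneal space will be chosen for all midline incisions where preperitoneal space can be safely and easily developed". Eligible operations are laparotomies and laparoscopic-assisted abdominal procedures in high-risk patients, and may be elective, urgent or emergent.

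Under Statistical analysis, the frequentist plan for these outcomes is "Secondary outcomes will be assessed either chi-square or Kruskal-Wallis test". For the primary outcome the plan adds a "multivariate regression analysis accounting for the 2 randomizations and the stratification". The Bayesian models take the same form and covariates, and "Similar models will be used for secondary outcomes". Neither pre-allocation time nor type of procedure is among the covariates.

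**The concern.** Nothing that happens before the allocation call can depend on the arm. If operative duration is taken in its ordinary sense, the measured quantity is the sum of a pre-allocation part, which carries no information about treatment, and a closure part, which carries all of it. The pre-allocation part depends on the underlying operation and can be expected to vary a good deal over this case mix. That variation enters the comparison as noise.

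Added time at closure is a practical cost of both interventions, and the trial plans to ask surgeons about barriers to using them. If the measure is too noisy to show a real cost of some minutes, a non-significant result may be read as evidence that the techniques add no operating time.

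**Working it through.** The plan gives no mean, SD, effect or power for operative duration, so it has no figure of its own to reproduce on this point.

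**Inputs from the plan**
- Number of patients N. The Statistical analysis section prints both 192 and 300 as the number enrolled, and 154 as randomized. Since 154/0.80 = 192.5, the 154 and 192 belong together under the stated 20% dropout. I use 154 and 300 as a bracket, with 300 × 0.80 = 240 between them.
- Alpha 0.05, taken as two-sided (the plan does not say which).
- A rank test for a continuous secondary outcome.

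**Assumptions (not in the documents)**
- A true added time of 10 minutes.
- Whole-operation SD of 30, 60 or 90 minutes; closure-time SD of 8 to 15 minutes.
- Comparison on one factorial margin, N/2 against N/2. The plan does not say whether Kruskal-Wallis compares margins or all four arms; four smaller arms would generally have less power for a main effect.

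**Step 1: analytic power.** Rank-test efficiency is taken as 3/π = 0.955, so

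power = Φ( 10 / (SD × √(4/(0.955 N))) − 1.96 ).

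The root is 0.165 at N = 154 and 0.118 at N = 300. Example, N = 154 and SD 60: 10/(60 × 0.165) = 1.01; 1.01 − 1.96 = −0.95; Φ = 0.17.

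**Step 2: simulation.** Pre-allocation time lognormal, mean 150 and SD 30, 60 or 90 minutes; closure time mean 20, SD 8; 10 minutes added in one group; Mann-Whitney test; 2,000 runs per setting. Simulated power is in brackets (N = 240 was not simulated).

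| N | Whole operation, SD 30 | SD 60 | SD 90 | Closure time, SD 8–15 |
|---|---|---|---|---|
| 154 | 52% (52%) | 17% (21%) | 10% (15%) | 98% or more |
| 240 | 71% | 24% | 13% | about 100% |
| 300 | 81% (81%) | 29% (37%) | 15% (26%) | about 100% |

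Simulated power is higher at the larger SDs because a rank test gains efficiency on skewed times. The simulated mean difference in total time was 10.0 to 10.2 minutes, and with no true difference the rejection rate was about 5%. The estimate is therefore unbiased, and only its precision suffers.

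**Step 3: smallest difference detectable with 80% power** = SD × √(4/(0.955 N)) × (1.96 + 0.84).
- Whole operation, SD 30 / 60 / 90: 13.9 / 27.7 / 41.6 minutes at 154; 9.9 / 19.9 / 29.8 at 300.
- Closure time, SD 8 / 10 / 15: 3.7 / 4.6 / 6.9 minutes at 154; 2.6 / 3.3 / 5.0 at 300.

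Conversely, a 10-minute cost reaches 80% power on whole-operation time only if the SD is at most about 10 × 30/13.9 ≈ 22 minutes at 154, or 10 × 30/9.9 ≈ 30 minutes at 300.

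**Step 4: could the stratum covariate close the gap?** Starting from SD 60, surgical approach would have to explain 1 − (30/60)² = 75% of the variance to reach SD 30 (needed at N = 300), and 1 − (22/60)² ≈ 87% to reach SD 22 (needed at N = 154).

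**The case against.** A reader might infer that measuring the whole operation hides or removes a real time cost. The documents do not support that. Randomization balances pre-allocation time on average, so the difference in total duration still estimates the added closure time; the simulation returned the 10 minutes put in.

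A reader might also infer that nearly all of the measured time precedes allocation, or that the trial will very likely report no difference. Both go beyond the documents, which define no start or stop point and give no operative times, closure times or SDs. Whole-operation time is the natural reading, but it is not stated. If the SD were about 30 minutes and 300 patients were randomized, a 10-minute cost would have 81% power. At SD 60 a cost of about 20 minutes would be detectable with 300.

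The plan also anticipates misreading of non-significant results. It adds Bayesian models with credible intervals and extends similar models to secondary outcomes. A wide interval around a positive estimate would show uncertainty and would not amount to a finding of no difference. This stands as a safeguard in reporting, but it does not restore the lost precision. The surgical-approach term may remove some variance, but not the variation between procedures within a stratum.

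Finally, total operating time has practical value of its own and is relevant to the hospital-perspective cost analysis. That is a good reason to keep reporting it.

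**Conclusion.** The point holds as one of definition and precision. Operative duration is undefined, allocation is at closure, both interventions act from then on, and no planned analysis isolates or adjusts for the time before allocation. On the ordinary reading, the comparison is unbiased but inefficient.

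The size of the loss depends on SDs and an effect that the documents do not give. Under the assumptions above, whole-operation time is adequate for a 10-minute cost only near the low end of the SD range and with the larger sample. Closure time is adequate at either sample size. The conflict between 154, 192 and 300 is a separate matter and does not alter this conclusion.

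The consequence is limited to how one secondary outcome may be read. Operative duration is in neither hypothesis and carries no power claim, and the primary analysis is unaffected. This is a minor improvement.

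**What to change.** 1. Give operative duration a stated start and stop point.
2. Have the study office log the time of the allocation call, and add closure time (allocation call to completion of closure, with the end point defined identically in every arm) as the time outcome used to compare arms. Starting at the call, not at the first fascial stitch, keeps mesh-plane preparation inside the measured interval.
3. Alternatively, record the same timestamp and adjust total duration for pre-allocation time in the regression and Bayesian models.
4. Keep total operative duration as a reported outcome, with an interval for the difference.
5. State whether the time comparison is made on the two factorial margins or across four arms.

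The cost is one timestamp and a few lines of text, with no added visit, staff or procedure. Any delay between the call and the start of closure adds slight noise.

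### The complication outcome has no severity cut: no by-arm comparison of Dindo-Clavien grade 3-5 events or of deaths is planned, although the protocol defines and reviews grade 3-5 as major

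*Combined protocol and SAP*

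**What the plan says.** The Methods paragraph on secondary outcomes reads: "Secondary outcomes will include any Dindo-Clavien complications, surgical site infections, reoperations, operative duration, patient centered outcomes, surgeon perceptions, and cost analyses". It gives no grade threshold, no time window and no rule for a patient with several events. Table 2 has Dindo-Clavien complications assessed at 1 month, 1 year and 3 years.

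The paragraph on the Data Safety Monitoring Board does use a severity cut: "All major complications (Dindo-Clavien 3-5) including deaths, reoperations, mesh explantations, and enterocutaneous fistulas will be reviewed". The trigger that follows is "Safety and stopping points will be determined based upon clinical judgment or greater than 50% rate of major complications"; it is not stated by arm. The same paragraph says "No interim analysis will be planned as analysis of the primary outcome will weaken the strength of the results".

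The Statistical analysis section has one sentence on frequentist tests for these outcomes: "Secondary outcomes will be assessed either chi-square or Kruskal-Wallis test". It does not assign a test to each outcome and does not mention grade. It adds Bayesian models for the primary outcome and says that similar ones will serve the secondary outcomes.

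Three related harms have their own place in Methods. Surgical site infection is a separate secondary outcome. So is reoperation: "Reoperation will be defined as any unplanned invasive procedure involving the fascia, mesh, or peritoneal cavity". Fistula sits in the primary outcome: "Persistent wound or infection will include any enterocutaneous fistula, open wound, or symptomatic fluid collection", counted when present at one year.

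**The concern.** The trial adds an implant in patients chosen for being at high risk, and both hypotheses concern benefit only. A recommendation on mesh or on small bites therefore needs an estimate of severe harm beside the estimate of benefit. The protocol has its own definition of severe harm, collects the grades and reviews the events, but plans no comparison on that definition.

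Read literally, the planned outcome counts a grade 1 event and a death alike. If minor complications are frequent, a rise in severe events moves the any-grade proportion less than it moves the grade 3-5 proportion. A severe event in a patient who already had a minor one does not move it at all. A result of no difference in complications could then be taken as reassurance about severe harm that the data do not give.

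**Working it through.** **No plan figure to reproduce.** The documents give no complication rates, so the calculation is illustrative. From the documents come the design, the sample sizes and the 20% dropout.

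**What is compared by arm.** Set the events named in the safety paragraph against the outcomes that are compared:

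- Reoperation: compared, as a secondary outcome.
- Mesh explantation: an unplanned surgical explantation falls within reoperation, but is not shown separately.
- Enterocutaneous fistula: compared within the primary outcome, if present at one year.
- Death: no outcome of its own. A death without reoperation or infection enters the secondary complication comparisons only through the any-grade outcome.
- Grade 3-5 total, organ failure, and invasive procedures outside the fascia, mesh and peritoneal cavity: likewise only through any-grade.

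**Patients per margin.** The sample-size sentence prints 192 and 300 enrolled side by side, and 154 randomized. 300 × 0.8 = 240, or 120 per margin; 154 / 2 = 77 per margin. Equal allocation is assumed.

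**Assumed rates.** Grade 3-5: 10% without mesh, 20% with mesh. Any grade without mesh (a0): 30%, 50% or 70%. The excess falls at random on patients with and without a minor event, so d = (0.20 − 0.10)/(1 − 0.10) = 0.111, and the any-grade risk with mesh is 1 − (1 − a0)(1 − d) = 37.8%, 55.6% or 73.3%.

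**Two-proportion power, two-sided 0.05.** With difference Δ and mean proportion p̄, SE0 = √(2p̄(1 − p̄)/n), SE1 = √((p1(1 − p1) + p2(1 − p2))/n), and power = Φ((Δ − 1.96·SE0)/SE1) + Φ((−Δ − 1.96·SE0)/SE1).

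- Grade 3-5, n = 120: SE0 = √(2 × 0.15 × 0.85/120) = 0.0461; SE1 = √((0.09 + 0.16)/120) = 0.0456; (0.10 − 0.0904)/0.0456 = 0.21; power 58%.
- Any grade from 50%, n = 120: Δ = 0.0556, SE0 = 0.0645, SE1 = 0.0644; (0.0556 − 0.1263)/0.0644 = −1.10; power 14%.

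**Chi-square on none / minor / major (2 df).** Noncentrality λ = n Σ (p0 − p1)²/(p0 + p1). For a0 = 50% the cells are 0.500/0.400/0.100 and 0.444/0.356/0.200, so λ = 120 × (0.00327 + 0.00261 + 0.03333) = 4.71; power 48%. The other two values of a0 give the same λ.

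| n per margin | Any grade, a0 = 30 / 50 / 70% | Rank test, three levels | Three-level chi-square | Grade 3-5 |
|---|---|---|---|---|
| 120 | 25 / 14 / 9% | about 30-35% (simulated) | 48% | 58% |
| 77 | 17 / 11 / 7% | about 21-24% (simulated) | 32% | 41% |

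**If the whole excess is an upgrade of existing minor events.** The any-grade difference is zero, so a yes/no test rejects only at its 5% error rate. The three-level chi-square does better: for a0 = 50%, λ = 120 × (0.01/0.7 + 0.01/0.3) = 5.71 and power is 56%; at 30% and 70% it is 72% and 51%. A rank test has about 10% (simulated, cells 60/30/10 against 60/20/20).

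**Other rates.** With grade 3-5 at 5% against 15%, and minor events independently in 20-40% of both arms, grade 3-5 has 54% power at N = 154 and 74% at N = 240; any grade has 11-20% and 15-28%.

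**Precision.** At 10% against 20%, the 95% interval for the grade 3-5 risk difference is about ± 1.96 × 0.0456 = ± 9 points at 120 per margin, and ± 1.96 × √(0.25/77) = ± 11 points at 77.

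**The case against.** The strongest reply is that most routes of mesh harm are already compared. Of the four events that the safety paragraph names, only death has no other compared outcome. That stands, and it limits the point. A reader might infer that severe events are never compared by arm; the documents do not support that.

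Second, the plan is unspecified, not committed to yes/no. Methods cites a graded classification, the safety paragraph uses it as graded, and the analysis section allows chi-square or Kruskal-Wallis. This also stands. A three-level chi-square recovers much of the loss, 48% against 58%, so a reader should not conclude that the planned comparison has no power for severe harm. That is true only of a yes/no analysis in the pure-upgrade case. But the choice is left open, and neither test gives a grade 3-5 risk difference.

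Third, the plan itself warns against false-negative conclusions and adds Bayesian estimates with credible intervals for secondary outcomes. This helps with interpretation, but those models would use the same undefined complication variable.

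Fourth, the frequency of minor complications and a doubling of severe ones are assumptions. They are; the direction of the dilution does not depend on the exact values, but its size does.

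A reader might also lean on the Background sentence "The use of synthetic materials in comorbid patients or complex settings may risk major wound complications such as prosthetic infection" as an admission of mesh risk. It does not serve: the trial mesh is biologic, and the next sentence there reports benefit from biologic materials.

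**Conclusion.** The point holds as a specification gap in a secondary outcome. The plan states no by-arm comparison of the grade 3-5 proportion or of deaths, and its any-grade outcome can hide an excess of severe events if analysed as yes/no. In the example, power at 120 per margin is 9-25% for any grade against 58% for grade 3-5; at 77 per margin it is 7-17% against 41%. These figures rest on assumed risks of 10% and 20%, equal allocation, an excess unrelated to minor events and a two-sided 5% test. The gap narrows to 48% against 58% if a three-level chi-square is used. The primary analysis is unaffected. The documents do not show that mesh or small bites cause severe harm, or that such harm would go wholly unseen.

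**What to change.** In the secondary outcomes paragraph of Methods, keep any-grade complications and add beside it, as a named safety outcome, *proportion of patients with at least one Dindo-Clavien grade 3-5 complication*, with its follow-up window stated.

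In Statistical analysis, state that this proportion is compared for mesh v no mesh and for small v large bites in randomized patients, with a risk difference and 95% interval from a model containing both randomizations and surgical approach. List deaths and mesh explantations by arm beneath it.

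The cost is a line or two in each section. The grades are already collected and the grade 3-5 events already reviewed, so no visit, data item or clinical rule changes. The downside is one more secondary comparison with modest power, about 41-58% in this example. It should be reported as an estimate with its interval, and a non-significant result should not be read as no difference.
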